## 7 STUDY DESIGN

### 7.1 Overall Study Design and Plan

This is a multinational, randomized, double-blind study comparing the efficacy and safety of a 300 mg dose of peramivir administered intramuscularly versus placebo in adults with uncomplicated acute influenza. Approximately 600 subjects will be randomized to treatment to ensure enrollment of approximately 450 subjects that are positive for influenza A. All subjects will be centrally randomized to 300 mg of peramivir or placebo in a ratio of 2:1 and will be stratified according to smoking status and RAT test for influenza A or B.

Study drug will be administered as bilateral 2mL intramuscular injections (total of 4mL injected in equally divided doses). Procedures for intramuscular injection, with a recommended needle length appropriate to the physical characteristics of the subject, are provided in the study drug administration manual.

Subjects eligible for screening will have an anterior nasal swab collected for testing by RAT for influenza A and B, in accordance with the commercially available RAT kit instructions. If the initial RAT is negative, the test should be repeated within one hour. Subjects meeting the inclusion/ exclusion criteria may be enrolled into the study.

All enrolled subjects will record the following information in a Study Diary.

- Assessment of the presence and severity of each of seven symptoms of influenza on a 4-point scale (0, absent; 1, mild; 2, moderate; 3, severe) twice daily (AM, PM) through Day 9 following treatment, then once daily (AM) through Day 14.
- Oral temperature measurements will be taken with an electronic thermometer every 12 hours. With the exception of the baseline measurement, all temperature measurements will be obtained at least 4 hours after, or immediately before, administration of oral acetaminophen (paracetamol) or other antipyretic medication.
- Assessment of subject's time lost from work or usual activities and rating of productivity compared to normal (rated as 0-10 on a visual analog scale) once daily through Day 14
- Doses of antipyretic, expectorant, and/or throat lozenges taken for symptomatic relief each day through Day 14

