#### **10.1.11 Subject Self Assessments**

Subject self assessments will be performed beginning pre-dose on Day 1 and recorded in the subject's Study Diary including the following:

- Oral temperature measurements with an electronic thermometer (provided by the Sponsor for the study) every 12 hours. With the exception of the baseline measurement, all temperature measurements will be obtained at least 4 hours after, or immediately before, administration of oral acetaminophen (paracetamol, provided) or other anti-pyretic medications. The times of each temperature determination will be recorded in the Study Diary. The baseline temperature will be recorded at the screening/Day 1 visit prior to dosing, regardless of whether the subject had recently taken an anti-pyretic.
- Assessment of seven influenza symptoms (cough, sore throat, nasal obstruction, myalgia [aches and pains], headache, feverishness, and fatigue) on a 4-point severity scale (0, absent; 1, mild; 2, moderate; 3, severe) twice daily, beginning pre-dose on Day 1 and through Day 9, then once daily through Day 14.
- Assessment of the subject's time lost from work or usual activities and productivity compared to normal using a 0-10 visual analogue scale once daily through Day 14.

The subject's diary card will be reviewed by study staff at each visit for completion of the record of all required items, with particular emphasis on alleviation of symptoms as well as relapse of symptoms. Relapse is defined as the recurrence of at least one respiratory symptom and one constitutional symptom (both greater than mild in severity) for 24 hours and the presence of fever (unless influenced by antipyretic use). Relapse can only occur after the subject has met the endpoint criteria for alleviation of symptoms. Study staff will not attempt to ask subjects to retrospectively complete missing diary card data for any scheduled assessments that have not been completed prior to the clinic visit. Study staff should, however, remind the subject to complete the diary card at all scheduled times.

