## Study Measurements and Visit Schedule Figure Legend

-  It is expected that the date of Screening and Day 1 (date of administration of study drug) will be the same. Visits at Screening and on subsequent study days may occur in subject's home by the investigator (all visits) or appropriately trained study center staff (Day 3, 5, 9 visits).
-  Day 2 will be a telephone contact with the subject to ensure compliance with diary card completion, concomitant medication and adverse event review.
-  If an IRC is suspected then a targeted physical examination will be conducted to record the presence/absence of the IRC.
-  Clinical laboratory assessments performed at Screening are for the purpose of establishing a baseline. Subject may be enrolled and begin treatment with study drug prior to receiving results. A PK sample will be drawn 30-60 minutes following the second treatment administration injection. On Day 3 an extra tube will be included with the safety blood sample to collect the second PK sample for evaluation of peramivir concentrations.
-  Vital sign measures will include blood pressure, pulse rate and respiration rate. Vital signs will be recorded at Screening, pre-dose and at 15 min following the study drug administration on Day 1, then once on remaining days as stipulated. The investigator will record oral temperature at baseline. Thereafter the subject will report oral temperature measurements twice daily in the Study Diary
-  If the baseline ECG is interpreted by the conducting physician as meeting the exclusionary criteria listed in section 8.1.2 the subject will not be enrolled in this study. If the ECG is interpreted as being abnormal and does not meet the exclusionary criteria (e.g. acute ischemia, medically significant dysrhythmia) then this subject may be enrolled if the conditions highlighted in section 10.1.5 are met for the subject.
-  Subjects record symptom assessment in Study Diary, twice daily, beginning pre-dose on Day 1 through Day 9, then once daily through Day 14. Subjects record time lost from work or usual activities and rating of productivity compared to normal once daily through Day 14. Subjects record oral temperature twice daily throughout as well as all influenza related medications.

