## 12.7 Efficacy Analyses

### 12.7.1 Primary Efficacy Endpoint

The primary efficacy endpoint is the time to alleviation of symptoms of influenza in subjects diagnosed with influenza, defined as the time from injection of study drug to the start of the time period when a subject has Alleviation of Symptoms. A subject has Alleviation of Symptoms if all of the seven symptoms of influenza (nasal congestion, sore throat, cough, aches and pains, fatigue (tiredness), headache, feeling feverish) assessed on his/her subject diary are either absent or are present at no more than mild severity level and at this status for at least 21.5 hours (24 hours - 10%).

Descriptive statistics for the primary efficacy variable will be tabulated by treatment group. Alleviation of symptoms will be determined by assessment of symptoms as reported on each subject's diary card. Time to alleviation of symptoms will be summarized for each treatment group (300 mg peramivir and placebo). Treatment comparisons between the 300 mg peramivir group and placebo will be assessed using a Wilcoxon-Gehan statistic stratified by smoking status and positive PCR or viral culture for influenza A or B at screening for the ITTI and PPI populations. Subjects who do not experience alleviation of symptoms will be censored at the date of their last non-missing post-baseline assessment.

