Subject's oral temperature will be summarized by study visit and treatment group. Differences between the 300 mg peramivir treatment group and placebo will be assessed using the van Elteren test controlling for smoking status and positive PCR or viral culture for influenza A or B at screening. A subject has Resolution of Fever if he/she has a temperature  $< 37.2^{\circ}\text{C}$  ( $99.0^{\circ}\text{F}$ ) and no antipyretic medications have been taken for at least 12 hours. The time to resolution of fever will be estimated using the method of Kaplan-Meier using temperature and symptom relief medication information obtained from the subject diary data. Differences between the treatment groups will be assessed using the Wilcoxon-Gehan statistic controlling for smoking status and positive PCR or viral culture for influenza A or B at screening. Subjects who do not have resolution of fever will be censored at the time of their last non-missing post-baseline temperature assessment.

The number and percentage of subjects experiencing influenza related complications will be summarized by complication preferred term and treatment group. The difference between the treatment groups (300 mg peramivir and placebo) will be assessed using a Cochran-Mantel-Haenszel (CMH) test statistic controlling for smoking status, and positive PCR or viral culture for influenza A or B at screening, if applicable.

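### Resolution of Fever rests on a single reading and on a 12-hour antipyretic-free test for which protocol version 4.0 specifies no dose times

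*Combined protocol and SAP*

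**What the plan says.** All references are to protocol version 4.0 unless stated.

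- **Event definition (12.7.2).** Fever has resolved when a temperature is below 37.2 °C and "no antipyretic medications have been taken for at least 12 hours". The time to this event is estimated "using temperature and symptom relief medication information obtained from the subject diary data" and compared between arms with a stratified Wilcoxon-Gehan test.
- **Temperatures (10.1.11).** The diary takes "Oral temperature measurements with an electronic thermometer (provided by the Sponsor for the study) every 12 hours". Clock times are explicit: "The times of each temperature determination will be recorded in the Study Diary". After baseline, a reading is to be taken either just before an antipyretic or 4 hours or more after one.
- **Antipyretics.** Section 7.1 asks for "Doses of antipyretic, expectorant, and/or throat lozenges taken for symptomatic relief each day through Day 14". The legend to Figure 1 says: "Subjects record oral temperature twice daily throughout as well as all influenza related medications". Neither asks for the clock time of a dose.
- **Pre-treatment antipyretics.** The baseline temperature is taken "regardless of whether the subject had recently taken an anti-pyretic", and the sentence ends there. In version 3.0 (10.1.11) the same sentence went on to require the time of any pre-treatment antipyretic in the CRF.
- **Comparison endpoint (12.7.1).** For the primary endpoint, symptoms must be "present at no more than mild severity level and at this status for at least 21.5 hours". Relapse (10.1.11) requires 24 hours.

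**The concern.** There are two separate weaknesses.

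First, the fever rule has no hold period. The first qualifying low reading is the event, whatever the next reading shows. Temperature can move up and down during an illness, so a trough can be scored as resolution.

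Second, the rule looks back 12 hours for antipyretic use, and that needs dose times. The protocol expects readings from 4 hours after a dose onward, and paracetamol is provided to subjects. Readings 4 to 12 hours after a dose will therefore be common, and they are the ones the 12-hour test must exclude. Without dose times they cannot be told apart from readings that qualify. The same holds just after injection, when the look-back runs into the period before treatment.

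Time to resolution of fever is one of only two secondary clinical endpoints (6.2.2), and it is formally tested. If premature events occurred in both arms, they would tend to blur a treatment difference. The primary endpoint is not affected.

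**Working it through.** The plan states no power, event rate or temperature variance for this endpoint, so there is no figure to reproduce. The check has three parts.

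**1. Can the 12-hour look-back be resolved from daily dose records?** Assume readings at 08:00 and 20:00; the protocol says only every 12 hours.

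| Reading | Look-back window | Hours on previous day | Hours on same day | Same-day hours outside window |
|---|---|---|---|---|
| 08:00 | 20:00 to 08:00 | 4 | 8 | 16 |
| 20:00 | 08:00 to 20:00 | 0 | 12 | 12 |

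A dose known only by its date may lie inside or outside either window. Take a reading of 37.0 °C at 08:00, one antipyretic logged that day and none the day before. If the dose was taken at 03:00, the reading comes 5 hours after it and does not qualify. If it was taken at 08:05, the reading qualifies. The daily record is identical. If any same-day dose disqualifies, resolution is delayed in the second case; if untimed doses are ignored, it is advanced in the first.

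The only time-imputation rule given (12.10.4) assigns 23:59 to daily diary values whose completion time is missing. It concerns diary completion, not dose time. If it were stretched to doses, one actually taken at 14:00 would leave the 20:00 reading that day counted (6 hours after the dose, wrongly). It would also exclude the 08:00 reading next day (18 hours after, wrongly).

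**2. How far does the pre-treatment gap reach?** For injections between 10:00 and 16:00, the look-back of a 20:00 reading starts at 08:00, which is 2 to 8 hours before injection. Example: antipyretic at 12:00, injection at 14:00, reading at 20:00. The interval since the antipyretic is 20 − 12 = 8 hours, so the reading should not count, yet nothing version 4.0 requires would show this. Any reading more than 12 hours after injection has a window lying wholly after treatment. The gap therefore concerns about one reading per subject.

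**3. How much could a single-reading rule matter?** Illustration only. Let p be the chance that one reading falls below 37.2 °C while the subject is still febrile, let q = 1 − p, and treat readings as independent. Over four readings (48 hours):

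- at least one low reading: 1 − q⁴
- at least two consecutive low readings: 1 − (q⁴ + 4pq³ + 3p²q²)

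With an assumed mean of 37.7 °C and SD 0.4 °C, z = (37.2 − 37.7)/0.4 = −1.25 and p = 0.106. The results are 1 − 0.894⁴ = 0.36 and 0.031.

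| Assumption | One low reading | Two in a row |
|---|---|---|
| Mean 37.5 °C, SD 0.4 °C | 64% | 13% |
| Mean 37.7 °C, SD 0.4 °C | 36% | 3% |
| Mean 38.0 °C, SD 0.4 °C | 9% | 0.2% |
| p = 0.05 | 18.5% | 0.7% |
| p = 0.10 | 34.4% | 2.8% |
| p = 0.20 | 59.0% | 10.4% |
| p = 0.30 | 76.0% | 21.6% |

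For p from 0.05 to 0.30, the single-reading chance runs from 9.8% to 51.0% over 24 hours and from 26.5% to 88.2% over 72 hours.

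**The case against.** A reader might infer that dose times are not collected at all. The documents do not show that. The diary form, the CRF pages and any separate SAP text are not in the file; they could hold a time field or a confirmation rule, and section 12.2 leaves technical detail to the SAP. What can be said is that version 4.0 does not specify dose times. That is still a gap, because a SAP can add a rule but cannot recover times that were never recorded.

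Pre-treatment use is not necessarily unrecorded either. Figure 1 marks concomitant medications at Screening and Day 1, and section 9.6 requires medications used during the study to be documented. Section 10.1.12, however, sends symptomatic medication to the diary, and none of these asks for a time. Nor is the change from version 3.0 an error in itself; what matters is that version 4.0 keeps the look-back without the entry that served it.

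The missing hold period can be defended as a design choice. The 21.5-hour rule governs a self-rated composite of seven symptoms, and nothing obliges a measured temperature to follow it. Requiring two qualifying readings would also demand about 24 antipyretic-free hours (12 before the first reading and 12 between them), so an afebrile subject taking paracetamol for aches would be scored as still febrile. This stands, and it is why the two-reading rule belongs in a sensitivity analysis and not in the main definition.

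**Conclusion.** The point holds in a limited form. Version 4.0 counts one unconfirmed reading as resolution. It attaches a 12-hour antipyretic condition that cannot be reliably applied from the data it specifies. A transient or drug-suppressed low reading may therefore be scored as resolution.

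Three stronger readings are not supported:

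- **That drug-masked fever is scored as resolved.** The rule itself bars any reading within 12 hours of an antipyretic. With untimed doses, the error may advance or delay the event, depending on a convention the protocol does not state.
- **That false resolutions cluster in the first day, where Wilcoxon-Gehan gives most weight.** Only the pre-treatment gap is confined to the first 12 hours. Troughs can occur at any time, and under the illustrative model they become rarer as mean temperature rises. No bias or loss of power in the treatment comparison has been shown.
- **That 36% is a false-resolution rate.** It rests on an assumed mean, an assumed SD and independent readings, and it ignores the antipyretic condition, which would remove some of these readings. At a mean of 38.0 °C, the oral fever threshold for entry, the figure is 9%. The table shows only that a confirming reading cuts the chance substantially across the assumed range.

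**What to change.** 1. **Data capture.** Add a column to the diary for the clock time of each antipyretic dose, and restore the CRF field for the time of the last pre-treatment antipyretic. This has to be in place before subjects are enrolled.
2. **Definition.** State in section 12.7.2 that the 12-hour look-back includes pre-treatment use, so that no reading counts until 12 hours after the last antipyretic. State also that a reading does not qualify when an untimed dose could fall in its window.
3. **Sensitivity analysis.** Prespecify a confirmed version: two consecutive readings below 37.2 °C, both meeting the antipyretic condition, timed at the first.

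The cost is one diary column, one CRF field and one extra analysis. Treating untimed doses as disqualifying will delay resolution for some subjects, but in a known direction. The confirmed version will also run late when a reading is missing or an antipyretic is taken for aches, so it should be read beside the main analysis and not in its place.

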### 12.7.3 Exploratory Endpoints

The MRU, MRU-related direct costs, and indirect costs attributable to days missed of work and work productivity and/or performance losses will be summarized by treatment group, smoking status, and positive PCR or viral culture for influenza A or B at screening, if applicable. Methods for describing differences between treatment groups will be presented in the SAP.

Genotypic (including Hemagglutinin and Neuraminidase), phenotypic, viral culture and PCR data will be listed for each subject. These listings will be constructed in a manner consistent with the FDA June 2006 Guidance Document: "*Guidance for Submitting Influenza Resistance Data*". Additionally, the number and percentage of genotypic changes from wild-type amino acid will be summarized separately for treatment group, protein type, and study visit.

## 12.8 Safety Analyses

AEs will be mapped to a MedDRA-preferred term and system organ classification. The occurrence of TEAEs will be summarized by treatment group using MedDRA-preferred terms, system organ classifications, and severity. If a subject experiences multiple events that map to a single preferred term, the greatest severity and strongest Investigator assessment of relation to study drug will be assigned to the preferred term for the appropriate summaries. All AEs will be listed for individual subjects showing both verbatim and preferred terms. Separate summaries of treatment-emergent SAEs and AEs related to study drug will be generated.

Descriptive summaries of vital signs and clinical laboratory results will be presented by study visit. Laboratory abnormalities will be graded according to the DAIDS Table for Grading Adverse Events for Adults and Pediatrics (Publish Date: December 2004). The number and percentage of subjects experiencing treatment-emergent graded toxicities will be summarized by treatment group. Laboratory toxicity shifts from baseline to Day 3, Day 5, and Day 14 will be summarized by treatment group.

Abnormal physical examination findings will be presented by treatment group. The number and percent of subjects experiencing each abnormal physical examination finding will be included.

Concomitant medications will be coded using the WHO dictionary. These data will be summarized by treatment group.

Subject disposition will be presented for all subjects. The number of subjects who completed the study and discontinued from the study will be provided. The reasons for early discontinuation also will be presented.

## 12.9 Sub-Study and Pharmacokinetic Analysis

A sub-study to collect pharmacokinetic samples in up to 60 peramivir treated subjects to examine exposure response will be conducted at selected sites. The data from the sub-study will be combined with the two PK samples (collected on all subjects at 30-60 minutes following administration of study drug and on study day 3) to perform a population exposure-response analysis. All analyses related to exposure-response will be completed as part of the sub-study. All statistical methods will be outlined as part of the sub-study protocol and exposure-response analysis plan. All sub-study analyses, and exposure-response analyses from PK samples obtained in this study and a companion study BCX1812-312, will be reported in a separate sub-study report.

## **12.10 General Issues for Statistical Analysis**

### **12.10.1 Multiple Comparisons and Multiplicity**

No adjustments for multiple comparisons are currently planned.

### **12.10.2 Covariates**

Primary and secondary efficacy analyses will be adjusted for smoking status and positive PCR or viral culture for influenza A or B at screening, where appropriate.

### **12.10.3 Planned Sub-Groups**

The primary efficacy endpoint will be summarized separately by smoking status and positive PCR or viral culture for influenza A or B at screening using descriptive statistics by treatment group and study day, where appropriate. No formal statistical testing will be utilized.

Additional analyses may be performed by country, if necessary, for submission to local regulatory authorities.

### **12.10.4 Missing Data**

Every effort will be made to obtain required data at each scheduled evaluation from all subjects who have been randomized. No attempt will be made retrospectively to obtain missing subject reported data (including influenza symptom severity assessments, temperature, ability to perform usual activities, missed days of work and impact of influenza on subject's work performance and/or productivity) that has not been completed by the subject at the time of return of the subject diary to the investigative site. In situations where it is not possible to obtain all data, it may be necessary to impute missing data.

In assessing the primary efficacy endpoint, for subjects who withdraw or who do not experience alleviation of symptoms, missing data will be censored using the date of subject's last non-missing assessment of influenza symptoms. Missing assessments of influenza symptoms conservatively will be imputed as having severity above absent or mild (as failures). For the subject diary data, the following data conventions will be utilized. Missing diary completion will be imputed as 11:59 for diary entries designated as morning and 23:59 for evening and daily reported values. Select exploratory sensitivity analyses may be conducted to ascertain the effect, if any, of these methods. These sensitivity analyses are further described in the SAP. Secondary efficacy endpoints with time to event data will be censored using the date of subject's last non-missing assessment of the given endpoint.

